4. STUDY DESIGN

4.1. Overall Design

This is a Phase 2, randomized, open-label, 2-arm study designed to evaluate the efficacy and safety of alternative dosing schedules of duvelisib treatment in subjects with R/R iNHL who have received at least 1 prior systemic therapy. This is a multi-site global study.

Subjects will be stratified by number of prior therapies (1 or > 1), bulky disease status (longest diameter of baseline lesion < 5 cm or ≥ 5 cm) and time since last recurrence (≥ 24 months or < 24 months).

Subjects will be randomized to Arm 1 or Arm 2 in a 1:1 fashion.

- Arm 1: duvelisib 25 mg BID for one 10-week cycle followed by 25 mg BID on Weeks 3 and 4 of each subsequent 4-week cycles until disease progression, unacceptable toxicity, or withdrawal.
- Arm 2: duvelisib 25 mg BID on Weeks 1, 2, 5, 6, 9 and 10 of one 10-week cycle, then on Weeks 3 and 4 of each subsequent 4-week cycles until disease progression, unacceptable toxicity, or withdrawal.

The study has a 2-stage design (see [Figure 2](#)). For each arm: in the first stage, 15 subjects will be enrolled. Responses will be assessed by the Investigator according to the 2007 revised IWG criteria ([Cheson 2007](#)) (primary endpoint) and the 2014 Lugano criteria ([Cheson 2014](#)). The evaluation of the first stage will take place after the enrolled subjects have been followed for a minimum of 3 cycles. If there are fewer than 6 responders (partial response [PR] or complete response [CR]) among the first 15 subjects per arm, consideration may be given to stopping that arm. Otherwise, approximately 36 additional subjects will be enrolled for a total of 51 per arm. Enrollment will be continuous between Stage 1 and Stage 2. If fewer than 22 (43%) responders (PR or CR) are observed in 51 subjects, consideration may be given to concluding that the treatment schedule does not warrant further study in this population.

It is anticipated that study enrollment will occur over approximately 2 years. The last subject visit will occur 2 years after the last subject is randomized.

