9.2. Sample Size Determination

The sample size for each arm was calculated using a 2-stage approach.

For each arm: in the first stage, 15 subjects will be randomized. The evaluation of the first stage will take place after the 15 enrolled subjects have been followed for a minimum of 3 cycles (18 weeks).

If there are fewer than 6 responders (PR or CR) among the first 15 subjects, consideration may be given to terminating the treatment arm. The decision to proceed to Stage 2 will be based on the totality of data observed, including types of responses, safety data, and discontinuation rates. The treatment arm may also not proceed to the second stage if the totality of the data is viewed as compelling; such scenarios could include (but are not limited to) accumulating enough data in Stage 1 to conclude the ORR exceeds 30%. If the treatment arm proceeds to the second stage, up to 36 additional subjects will be enrolled for a total of 51. If fewer than 22 (43%) responders (PR or CR) are observed in 51 subjects, consideration may be given to concluding that the treatment schedule does not warrant further study in this population. The final evaluation of each schedule will be based on the totality of data observed, including types of responses, safety data, and discontinuation rates. This design yields 90% power under the assumptions described above; the alpha level (type I error rate) for the study will be controlled at 0.025.

Subjects will be stratified by number of prior therapies (1 or > 1), bulky disease status (longest diameter of baseline lesion < 5 cm or ≥ 5 cm) and time since last recurrence (≥ 24 months or < 24 months).

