9.4.1. General Considerations

Each treatment arm will be evaluated separately; no formal comparisons between treatment arms are planned. Hypothesis testing will be used for the primary efficacy endpoint of ORR for each treatment arm. No formal hypothesis testing will be used for any other endpoints or other study data, such as demographics and safety data.

Tabulations will be produced for appropriate disposition, demographic, baseline, efficacy, and safety parameters. For categorical variables, summary tabulations of the number and percentage of subjects within each category (with a category for missing data) of the parameter will be presented, as well as 2-sided 95% CIs, unless stated otherwise. For continuous variables, the number of subjects, mean, median, standard deviation, minimum, and maximum values will be presented. Time-to-event data will be summarized using Kaplan-Meier (KM) methodology using 25th, 50th (median), and 75th percentiles with associated 2-sided 95% CIs, as well as number and percentage of censored observations.

The Investigator's assessments of disease response will be used as the basis for the evaluation of the primary and secondary efficacy endpoints.

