9.4.2. Primary Endpoint Efficacy Analysis

The ORR (proportion of subjects achieving a CR or PR) will be estimated, along with the 2-sided 95% exact CI. Responses for the primary ORR analysis will be assessed using the 2007 revised IWG criteria ([Cheson 2007](#)). Missing data will be imputed by assuming that any subjects not exhibiting a response (CR or PR) are non-responders.

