9.5. Interim Analyses

There is no formal interim analysis. Study data for each arm will be evaluated at the end of Stage 1 to determine whether a study arm should be terminated or continued to Stage 2. Please see additional details of the 2-stage design in Section [9.2](#).

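### No stated criterion rejects ORR ≤30%: the 22/51 count behind the quoted alpha and power disagrees with the planned exact 95% CI, which needs 23/51

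*Protocol*

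**What the plan says.** **Hypotheses and testing.** Protocol 9.1 and SAP 4.10.1 set ORR ≤30% against ≥55% for each arm. Protocol 9.4.1 adds: "Hypothesis testing will be used for the primary efficacy endpoint of ORR for each treatment arm".

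**Operating characteristics.** Protocol 9.2 gives 90% power and states that "the alpha level (type I error rate) for the study will be controlled at 0.025". SAP 4.13 gives the same two figures and calls the 0.025 one-sided. SAP 4.10.1.4 analyses the arms separately without multiplicity adjustment.

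**Stage 1.** With fewer than 6 responders among 15, "consideration may be given to terminating the treatment arm" (Protocol 9.2). The decision to continue rests on the totality of the data. An arm may also stop if the data are compelling, for example after "accumulating enough data in Stage 1 to conclude the ORR exceeds 30" percent. Protocol 9.5 says "There is no formal interim analysis", and SAP 4.10.1.5 agrees. Protocol 4.1 says "Enrollment will be continuous between Stage 1 and Stage 2".

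**End of Stage 2.** "If fewer than 22 (43%) responders (PR or CR) are observed in 51 subjects, consideration may be given to concluding" that the schedule does not merit further study (Protocol 9.2; the same rule is in Protocol 4.1 and SAP 3.1 and 4.13). The final evaluation again rests on the totality of the data.

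**Primary analysis.** In Protocol 9.4.2 the ORR "will be estimated, along with the 2-sided 95% exact CI". SAP 4.10.2 names Clopper-Pearson, with the mITT set as denominator.

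**The concern.** A test is promised and an error rate is claimed for it, but no p-value threshold, critical count or confidence-limit rule says when the null is rejected. Two candidates can be read out of the text, the 22/51 count and the exact CI, and they give different answers at exactly 22 responders. The quoted alpha and power also presuppose that arms below 6/15 always stop, which the text does not require.

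The alpha and power that apply therefore depend on a sentence that is missing. In an open-label trial with investigator-assessed response, a success rule left open can be settled after the counts are known. The unbounded Stage 1 route raises the same question: it is unclear whether closing an arm for compelling data amounts to rejecting the null.

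**Working it through.** **Inputs.** p0 = 0.30 and p1 = 0.55 (Protocol 9.1); n1 = 15, continue at 6 or more; 36 further subjects, n = 51; final count 22 (Protocol 9.2); two-sided 95% Clopper-Pearson interval (SAP 4.10.2). All error rates are one-sided and per arm.

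**Formulas.** Let X1 ~ Bin(15, p) and X2 ~ Bin(36, p).

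- Stop always applied, final cut r: P(reject) = Σ over x = 6 to 15 of P(X1 = x) · P(X2 ≥ r − x).
- Stop never applied: P(reject) = P(Bin(51, p) ≥ r).

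Alpha is the value at p = 0.30, power the value at p = 0.55.

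**Step 1: reproduce the plan.** With r = 22 and the stop always applied, alpha = 0.0246 and power = 0.9035. These match the stated 0.025 and 90%. A search over two-stage designs of up to 56 subjects with alpha ≤0.025 and power ≥0.90 gives 6/15 then 22/51 as the one with the smallest expected sample size under the null (25.0). This is evidently the design behind the figures.

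**Step 2: what the exact CI requires.**

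| Responders | Exact 95% CI | Excludes 30%? |
|---|---|---|
| 22/51 | 29.3% to 57.8% | No |
| 23/51 | 31.1% to 59.7% | Yes |

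**Step 3: both rules, by how the stop is used.**

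| 6/15 stop | Alpha, 22/51 | Power, 22/51 | Alpha, 23/51 (CI) | Power, 23/51 (CI) |
|---|---|---|---|---|
| Always applied | 0.0246 | 90.4% | 0.0132 | 88.4% |
| Arms at exactly 5/15 continue, lower counts stop | 0.0291 | 94.8% | 0.0151 | 92.4% |
| Never applied | 0.0319 | 96.7% | 0.0161 | 94.1% |

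Stopping can only remove rejections, so 0.0319 and 0.0161 are upper bounds for a final test at n = 51. Under the CI rule, power falls below 90% only if more than (0.94051 − 0.90)/(0.94051 − 0.88428) = 72% of the arms below 6/15 are stopped, assuming the chance of stopping is the same for every count from 0 to 5.

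**Step 4: how often the two rules disagree.** They differ only at exactly 22/51. The 45% column is an assumed intermediate value, not one from the documents.

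| Stop | ORR 30% | ORR 45% | ORR 55% |
|---|---|---|---|
| Never applied | 1.6% | 10.8% | 2.7% |
| Always applied | 1.1% | 7.8% | 1.9% |

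**Step 5: the Stage 1 efficacy route.** No boundary is given. Assume for illustration that rejection is claimed at 9/15, the smallest count whose exact CI excludes 30% (lower limit 32.3%; at 8/15 it is 26.6%). Then alpha = P(X1 ≥ 9) + Σ over x below 9, from 6 if the stop is applied or from 0 if not, of P(X1 = x) · P(X2 ≥ r − x). With r = 23 this is 0.0255 (stop applied) or 0.0284 (not applied). With r = 22 it is 0.0353 or 0.0425.

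**The case against.** The arithmetic in Protocol 9.2 is right for the design it came from, and 0.0319 is a worst case: it treats 22/51 as the test and never stops an arm below 6/15, although 72% of arms with a true ORR of 30% would fall there. The natural reading is that the CI is the test. SAP 4.10.1 puts the null and the exact interval in one paragraph, and a one-sided 0.025 corresponds to a two-sided 95% interval. On that reading alpha is controlled with or without the stop. The rules part company at one count only, the study is a proof of concept, and the final judgement rests on the totality of the data. The Stage 1 figures need a boundary that the plan does not contain.

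Much of this stands. There is no calculation error, 0.0319 is conditional, the 9/15 boundary is an assumption, and the 45% column in Step 4 lies near the peak for this count (22/51 = 43%). It does not remove the gap. If the CI is the test, the quoted power is not that test's, and 22/51 is a benchmark that the primary analysis contradicts. If 22/51 is the test, control at 0.025 needs a stop that the text leaves optional. A plan that claims formal alpha control has to say which applies.

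**Conclusion.** The concern holds: the primary decision rule is missing, and the stated alpha, power and count belong to a design that the written rules do not impose. Per arm, alpha lies between 0.0246 and 0.0319 under a 22/51 rule and between 0.0132 and 0.0161 under the CI rule. Power at 55% lies between 90.4% and 96.7%, or between 88.4% and 94.1%. Power is a minor matter: the shortfall against 90% is at most 1.6 points at n = 51.

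These figures assume 51 treated subjects per arm and a Stage 1 count fixed on 15 subjects. Enrollment does not pause between stages, and SAP 4.10.2 places the primary ORR analysis 12 months after the last randomization, so late responses would shift the figures with the stop applied. They would not change the never-applied upper bounds. This should be fixed; it does not undermine the sample size.

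**What to change.** Amend Protocol 9.2 and SAP 4.13, with matching text in Protocol 4.1 and SAP 3.1:

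1. For an arm that completes Stage 2, reject the null only if the lower limit of the two-sided exact 95% CI for ORR is above 30% at the actual mITT n (23 or more responders at n = 51). Either label 22/51 as a go/no-go guide that is not the test, or change it to 23/51.
2. Call the 6/15 futility rule non-binding.
3. Report an arm closed at Stage 1, including for compelling data, by estimate and CI with no formal rejection.
4. In Protocol 9.2, describe alpha as one-sided and per arm, as the SAP does. Restate the properties at n = 51: alpha 0.016, and power at 55% of 94.1% if futility is not enforced or 88.4% if it is always obeyed.

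The rule carries over to nearby sample sizes:

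| mITT n | Responders needed | Alpha (not enforced) | Power (not enforced) | Power (always obeyed) |
|---|---|---|---|---|
| 48 | 22 | 0.0149 | 92.2% | 87.1% |
| 49 | 22 | 0.0195 | 94.1% | 88.5% |
| 50 | 23 | 0.0123 | 92.2% | 87.0% |
| 51 | 23 | 0.0161 | 94.1% | 88.4% |

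The cost is a few sentences, one more responder at n = 51 and no extra patients. If futility is always obeyed, power is 88.4% instead of 90.4%.

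The alternative is to make 6/15 binding and 22/51 the test. That keeps the stated figures, but the stop would have to be enforced despite continuous enrollment, and the ordinary exact CI would still disagree at 22/51.

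Because the trial is open-label and the SAP was revised in 2023 after a dry run, record when the rule was chosen and what response data were known by then. Of the two counts, 23/51 is the stricter.

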9.1. Statistical Hypotheses

This study will test the null hypothesis that the ORR for each arm is $\leq 30\%$ against the alternative that ORR is $\geq 55\%$.

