#### 4.10.1.4 Multiple Comparisons/Multiplicity

Each treatment arm will be analyzed separately with no adjustment for multiplicity.

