### 4.13 Determination of Sample Size

The sample size for each arm was calculated using a 2-stage approach.

For each arm: in Stage 1, 15 subjects will be randomized. The evaluation of the first stage will take place after the 15 enrolled subjects have been followed for a minimum of 3 cycles (18 weeks).

If there are fewer than 6 responders (PR or CR) among the first 15 subjects, consideration may be given to terminate the treatment arm. The decision to proceed to Stage 2 will be based on the totality of data observed, including types of responses, safety data, and discontinuation rates. The treatment arm may also not proceed to Stage 2 if the totality of the data is viewed as compelling;

such scenarios could include (but are not limited to) accumulating enough data in Stage 1 to conclude the ORR exceeds 30%. If the treatment arm proceeds to Stage 2, up to 36 additional subjects will be enrolled for a total of 51. If fewer than 22 (43%) responders (PR or CR) are observed in 51 subjects, consideration may be given to conclude that the treatment schedule does not warrant further study in this population. The final evaluation of each schedule will be based on the totality of data observed, including types of responses, safety data, and discontinuation rates. This design yields a type I error rate of 0.025 (1-sided) and power of 90% under the assumptions described above.

Subjects will be stratified by number of prior therapies (1 or  $> 1$ ), bulky disease status (longest diameter of baseline lesion  $< 5$  cm or  $\geq 5$  cm) and time since last recurrence ( $\geq 24$  months or  $< 24$  months).

Note: "Enrolled" means subjects', or their legally acceptable representative's, agreement to participate in a clinical study following completion of the informed consent process. Potential subjects who are pre-screened for the purpose of determining eligibility for the study but do not sign an informed consent form (ICF) are not considered enrolled.

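### Protocol 9.2 presents 0.025 as the type I error for the study, but it is a one-arm rate that relies on an optional futility rule; across two unadjusted arms it is about 0.049 if both are truly at 30%

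*Protocol*

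**What the plan says.** Protocol 9.1 sets one null per arm: "This study will test the null hypothesis that the ORR for each arm is" at most 30%, against an alternative of at least 55%. Protocol 9.4.1 repeats the scope: "Hypothesis testing will be used for the primary efficacy endpoint of ORR for each treatment arm". SAP 4.10.1.4 adds: "Each treatment arm will be analyzed separately with no adjustment for multiplicity".

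Protocol 9.2 sizes each arm by a two-stage rule with 15 subjects and then up to 36 more. With fewer than 6 responders among the first 15, "consideration may be given to terminating the treatment arm". At the end, "If fewer than 22 (43%) responders (PR or CR) are observed in 51 subjects, consideration may be given to concluding" that the schedule does not merit further study. The same section gives 90% power and then says that "the alpha level (type I error rate) for the study will be controlled at 0.025". SAP 4.13 describes the same rule but does not mention the study: "This design yields a type I error rate of 0.025 (1-sided) and power of 90% under the assumptions described above".

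For the analysis itself, Protocol 9.4.2 says that the ORR "will be estimated, along with the 2-sided 95% exact CI". SAP 4.10.2 names the Clopper-Pearson method. Neither section says which result rejects the null. Protocol 1.2 and 9.2 and SAP 3.1 and 4.13 also allow an arm to stop after Stage 1 on compelling data. Their example is having enough data to conclude that the ORR is above 30%.

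**The concern.** This is the only formal hypothesis test in the study, so its stated error rate should be the one the design has. A reader of Protocol 9.2 would take 0.025 as the chance that the study wrongly declares any schedule active. The rest of the plan describes two separate tests and no procedure that would hold the joint error at 0.025.

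Three things the rate depends on are also left open. The futility rule that brings the error below 0.025 is optional. The result that rejects the null is not named. And the Stage 1 example uses the null value itself, without saying whether such a stop counts as a rejection.

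**Working it through.** **Inputs.** Null rate 0.30 and alternative 0.55 (Protocol 9.1). Stage 1 has 15 subjects and continues with 6 or more responders. Stage 2 adds 36 for a total of 51, and the final cut-off is 22 (Protocol 9.2). There are two tests (Protocol 9.4.1) with no adjustment (SAP 4.10.1.4). The arms contain different subjects, so the tests are treated as independent.

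**Step 1: reproduce the plan's figures for one arm.** With the futility rule followed and no early success,

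P(success | p) = Σ (x = 6 to 15) P(X₁ = x; 15, p) × P(X₂ ≥ 22 − x; 36, p)

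- p = 0.30: 0.0246
- p = 0.55: 0.9035

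These match the stated 0.025 and 90%, so both are one-arm figures.

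**Step 2: two arms, both truly at 30%.** The chance of at least one false positive is 1 − (1 − a)².

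- Exact level: 1 − (1 − 0.0246)² = 0.0486
- Nominal level: 1 − (1 − 0.025)² = 0.0494

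Both are about 0.049, roughly twice the stated rate. If only one arm is null, the error is the per-arm value.

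**Step 3: the optional futility rule.** At a true 30%, Stage 1 falls below 6 of 15 with probability 0.722, so the rule would often come into play. If it is never applied, the per-arm error is P(X ≥ 22; 51, 0.30).

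| Futility rule, final cut-off 22 of 51 | Error per arm | Across two null arms | Power per arm |
|---|---|---|---|
| Always followed | 0.0246 | 0.049 | 0.904 |
| Followed half the time | 0.0282 | 0.056 | – |
| Never followed | 0.0319 | 0.063 | 0.967 |

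The half-way error is the average of the other two: (0.0246 + 0.0319)/2 = 0.0282.

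**Step 4: cut-off and confidence interval.** The Clopper-Pearson 95% lower limit is 29.3% at 22/51 and 31.1% at 23/51. The interval treats the 51 subjects as one sample and ignores the Stage 1 rule. It therefore need not agree with a two-stage cut-off.

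**Step 5: a Stage 1 efficacy claim (illustration).** The plan gives no boundary. *Assume* 9 or more of 15, the smallest count whose exact lower limit (32.3%) exceeds 30%; at 8 of 15 the limit is 26.6%. That claim alone has a false-positive chance of P(X ≥ 9; 15, 0.30) = 0.015 per arm. Added to the 22/51 rule with futility followed, the error becomes 0.035 per arm and 1 − (1 − 0.0353)² = 0.069 across two null arms.

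**The case against.** The strongest reply is that context settles the scope. Protocol 9.2 opens by saying that each arm was sized separately, 9.1 and 9.4.1 speak of each arm, the SAP openly declines to adjust, and SAP 4.13 does not say *for the study*. Two separately evaluated schedules in a proof-of-concept study can reasonably go unadjusted. This stands as a defence of the design, and nothing here asks for an adjustment. It does not make the sentence in Protocol 9.2 correct.

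Four stronger readings are tempting, and the documents do not support them.

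- *The 90% power is also misstated.* Protocol 9.2 attributes power to the design it has just described for each arm, and the figure reproduces.
- *The plan gives two contradictory answers at 22 of 51.* That follows only if the exact interval is the test. Both documents say that the ORR is estimated along with an interval, and neither makes the interval the rejection rule. What stands is that the rule is not stated.
- *The plan contains a hidden interim efficacy test.* Protocol 9.5 says there is no formal interim analysis, and SAP 4.10.2 schedules one primary ORR analysis. A Stage 1 stop can be read as a decision about enrolment only. What stands is that no section says so.
- *The futility rule's looseness is concealed.* Its optional status is stated openly, and 0.032 is the extreme in which it is never applied.

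**Conclusion.** The point holds as an error in the stated rate. For each arm, 0.025 is right, one-sided, if the futility rule is followed, success means 22 or more of 51, and Stage 1 yields no efficacy claim. As a rate for the study it is wrong: about 0.049 if both arms are truly at 30%. Without the futility rule the figures are 0.032 per arm and 0.063 across arms, so even the per-arm claim then fails.

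These figures assume independent arms and exactly 51 analysed subjects per arm. The plan's enrolment numbers are approximate, and the denominator is subjects dosed. The Stage 1 efficacy figures rest on an assumed boundary and are illustrative only.

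The matter should be fixed, but it does not undermine the trial. The study is a Phase 2 proof of concept, its conclusions are to rest on the totality of the data, and the correction changes no procedure.

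**What to change.** 1. **Error statement.** In Protocol 9.2, replace the words saying that alpha for the study is controlled at 0.025 with: *is 0.025 one-sided for each arm, with no adjustment across the two arms (about 0.05 if both arms are null), given that the Stage 1 futility rule is followed and success is 22 or more of 51; it is up to 0.032 per arm if the futility rule is not followed*. In SAP 4.13, add *for each arm* to the error and power sentence.
2. **Rejection criterion.** In Protocol 9.4.2 and SAP 4.10.2, name 22 or more of 51 as the result that rejects the null. Add that the exact 95% interval is descriptive and does not account for the two-stage rule, and that its lower limit at 22/51 is 29.3%.
3. **Stage 1 stop.** In Protocol 1.2 and 9.2 and SAP 3.1 and 4.13, delete the example of concluding that the ORR exceeds 30%. Alternatively, state that stopping an arm after Stage 1 is an enrolment decision, that the arm is then reported descriptively, and that it does not reject the null at any analysis.

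Requiring the exact interval to exclude 30% (23 or more of 51) may look simpler, but it is not recommended here. It moves the design cut-off and lowers power to 0.884 with futility followed. Its per-arm error of at most 0.016 holds at 51 subjects but not at nearby sizes: without a futility stop, the same interval criterion gives 0.021 at 52 and 0.023 at 47. If an arm stopped at 9 or more of 15 (again an assumed boundary) were also judged by its interval, the error would be 0.0255 per arm with futility followed and 0.0284 without.

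**Cost.** Wording only, with no added patients or visits. The stated study-level rate becomes less favourable, and the sponsor gives up an efficacy claim from Stage 1 alone.
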